**ML42362: NEOADJUVANT ATEZOLIZUMAB IN SURGICALLY RESECTABLE ADVANCED CUTANEOUS SQUAMOUS CELL CARCINOMA**

Document History	Notes
Version 3 Date: 14 Sep 2020	Initial Approval from Genentech
Version 4 Date: 29 Oct 2020	
Revision includes:
 
 
• Addition of information in regulatory considerations regarding the study drug, i.e. reasons why it is IND-exempt
 
• Formatting changes
 

Version 5 Date: 30 Oct 2020	
Revision includes:
 
 
• Formatting changes, updating ToC
 
• Correcting spelling and grammatical errors
 

Version 6 Date: 30 Oct 2020	
Revision includes:
 
 
• Formatting changes
 
• Clarification of the primary objective in the statistical plan
 

Version 7 Date: 04 Nov 2020	
Revision includes:
 
 
• Modified data safety and monitoring plan, including adding a stopping rule
 
• Updated the statistical plan
 

Version 8 Date: 12 Nov 2020	
Revision includes:
 
 
• Updated the statistical plan including expanding on outcome measures (primary and secondary)
 

Version 9 Date: 05 Mar 2021	
Revision includes:
 
 
• Updated the AE reporting timeline to Genentech from 15 calendar days to 30 days and clarified site responsibilities for signal management/ risk management for per feedback from Genentech
 

Version 10 Date: 06 Jul 2021	
Revision includes:
 
 
• Formatting and topological changes
 
• Added [name] as Co-Investigator
 
• Updated Section 4.2 
 
○ Clarified sources for Medical History
 
 
 
• Updated Section 4.4 
 
○ Clarified vital sign data collection
 
 
 
• Updated Section 4.5 
 
○ Clarified Screening Scan
 
 
 
• Updated Section 5.3
 

Document History	Notes
	
 
○ Clarified study drug storage and dispensation.
 
● Updated Section 7.2 
 
○ The number of allotted active patients has been increased from three to six based on contemporary subject safety data.
 
 
 
● Updated Section 7.3.1 
 
○ Clarified AE collection
 
 
 
● Clarified Procedures in Section 9 
 
○ Clarified pre-infusion vital sign collection window, screening TSH, and RECIST.
 
 
 

Version 11 Date: 16 Mar 2022	
Revision includes:
 
 
● Clarify language 
 
○ Section 12.3 language has been consolidated with section 7.2 to reflect previous amendment to six patients.
 
 
 
● Minor formatting and administrative changes
 
● Update Section 9 Study Calendar 
 
○ Footnote J: Screening lab window extended to 28 days to match Inclusion criteria #7
 
○ Screening window clarified to within 28 days prior to start of treatment
 
 
 
● Personnel changes 
 
○ Remove [name] as study coordinator
 
○ Add [name] study coordinator
 
 
 

Version 12 Date: 16 MAY 2022	
Revision includes:
 
 
● Clarify language 
 
○ Section 4.5 language to clarify collection of tumor response evaluations
 
○ Section 9 Study Calendar footnote P & S to clarify collection of RECIST measurements
 
 
 

Document History	Notes
Version 13 Date: 06 DEC 2022	
Revision includes:
 
 
• Minor formatting changes
 
• Updated Section 3 
 
○ Clarified section by removing limit of 25 patients that can be screened for study as this was an arbitrary number.
 
 
 
• Updated Appendix I 
 
○ Added management guidelines for 
 
▪ Immune-mediated Myelitis
 
▪ Immune-mediated facial paresis
 
 
 
○ Updated management guidelines for 
 
▪ Table 1: Pulmonary Events
 
▪ Table 4: Endocrine Events
 
▪ Table 6: Immune-related myocarditis
 
▪ Table 7: Infusion-related Reactions and Cytokine-release Syndrome
 
▪ Table 9: Dermatologic Events
 
▪ Table 10: Neurologic Disorders
 
▪ Table 12: Renal Events
 
▪ Table 13: Immune-mediated Myositis
 
▪ Table 14: Suspected Hemophagocytic Lymphohistiocytosis or Macrophage activation Syndrome
 
 
 
○ Updated Infusion related reactions subsection to "Infusion-related Reactions And Cytokine-Release Syndrome" and added updated information
 
○ Updated Dermatologic events subsection with updated information
 
 
 

Document History	Notes
	
 
○ Updated Lymphohistiocytosis and macrophage activation syndrome subsection with updated information
 
○ Added new references
 

Version 14 Date: 29 AUG 2023	
Revisions include:
 
 
• Minor formatting edits
 
• Administrative edits
 
• Updated Appendix G 
 
○ Added autoimmune myelitis to list of autoimmune disease that would exclude a patient from trial.
 
 
 
• Updated Appendix I 
 
○ Added missing table header for Table 11: Management Guidelines for Immune-Mediated Myelitis
 
○ Revised management guideline table numbering for 
 
▪ Table 12: Immune-Mediated Meningoencephalitis
 
▪ Table 13: Renal Events
 
▪ Table 14: Immune-Mediated Myositis
 
 
 
○ Updated management guidelines tables with information from IBv19 and associated addendum: 
 
▪ Tables 1-15
 
 
 
○ Updated references
 
 
 

Version 15 12AUG2024	
Revision includes:
 
 
• Updated Section 1.2 
 
○ Updated secondary objective to clarify that changes in surgery will be measured by intensity of surgery performed and cost of care.
 
 
 

**ML42362: NEOADJUVANT ATEZOLIZUMAB IN SURGICALLY  
RESECTABLE ADVANCED CUTANEOUS SQUAMOUS CELL CARCINOMA**

## PROTOCOL SYNOPSIS

TITLE	Neoadjuvant Atezolizumab in Surgically Resectable Advanced Cutaneous Squamous Cell Carcinoma
STUDY PHASE	N/A Feasibility study
INDICATION	Cutaneous Squamous Cell Carcinoma
INVESTIGATIONAL PRODUCT OR PROCEDURE	Atezolizumab (RO5541267)
PRIMARY OBJECTIVE	
 
Determine the feasibility of three doses of atezolizumab prior to surgery in patients with advanced cutaneous squamous cell carcinoma
 

SECONDARY OBJECTIVES	
 
Assess response rates to neoadjuvant atezolizumab 
 
Objective response rate following completion of neoadjuvant therapy based on RECIST 1.1 criteria
 
Pathological response rate (major and complete pathological response) in final surgical resection specimen
 
 
 
Assess change in surgical plan, as measured by intensity of surgery performed, cost of care, surgical margins or vital structures preserved, following neoadjuvant treatment
 
Assess safety and tolerability of neoadjuvant atezolizumab
 

EXPLORATORY OBJECTIVES	
 
Perform correlative studies to assess pre-treatment biological markers, including PD-L1 expression, that are associated with response to atezolizumab
 
Evaluate tumors prior to and during treatment to identify neoantigen profile changes and T-cell receptor repertoire changes
 
Evaluate changes in cell-free DNA, cytokine profiles associated with immune system activation, and lymphocyte subpopulations before and during treatment
 
Analysis of genes or gene signatures associated with tumor immunobiology
 

TREATMENT SUMMARY	Subjects will receive neoadjuvant atezolizumab (1200 mg). Atezolizumab will be administered by intravenous (IV) infusion

	at a fixed dose of 1200 mg on Day 1 (+/- 3 days) of each 21-day cycle for a total of 3 doses prior to surgery, unless there is clinical or radiographic evidence of disease progression.
SAMPLE SIZE	20 evaluable patients
STATISTICAL CONSIDERATIONS	See stats section

## SCHEMA

## LIST OF ABBREVIATIONS AND DEFINITION OF TERMS

Abbreviation	Definition
AJCC	American Joint Committee on Cancer
aPTT	Activated partial thromboplastin time
CR	Complete response
cSCC	Cutaneous squamous cell carcinoma
CT	Computed tomography
DSMC	Data Safety Monitoring Committee
ECG	Electrocardiogram
FDA	U.S. Food and Drug Administration
GCP	Good Clinical Practice
GI	Gastrointestinal
HBcAb	Hepatitis B core antibody
HBV	Hepatitis B virus
IB	Investigator's Brochure
ICH	International Conference on Harmonization
Ig	Immunoglobulin
IgG	Immunoglobulin G
IND	Investigational New Drug
IRB	Institutional Review Board
IRR	Infusion-related reaction
IV	Intravenous
LPLV	Last patient, last visit
NCI CTCAE	National Cancer Institute Common Terminology Criteria for Adverse Events
ORR	Overall response rate
OS	Overall survival
PK	Pharmacokinetic
PDL1	Programmed death-ligand 1
RECIST	Response evaluation criteria in solid tumors
ULN	Upper limit of normal
U.S.	United States

## 1. OBJECTIVES

### 1.1. Primary Objective

The primary objective is to determine the feasibility of three doses of atezolizumab prior to surgery in patients with advanced cutaneous squamous cell carcinoma. The primary outcome measure for each patient is an indicator for successfully completing 3 cycles of neoadjuvant atezolizumab, followed by surgical resection of remaining disease. The treatment will be evaluated as non-feasible for patients who have disease progression during neoadjuvant treatment, discontinue study medications due to toxicity, or are not able to undergo curative surgical resection after 3 cycles of treatment.

This study will gather safety and efficacy data to design a larger, more definitive trial that assesses important clinical endpoints including whether surgical margins can be reduced without compromising local control, the impact of neoadjuvant treatment on disease recurrence rates, and the role of adjuvant radiation and immunotherapy in high-risk patients. This study will also validate the neoadjuvant approach. If the neoadjuvant approach is feasible, this study may allow for the addition of an additional cohort that evaluates the potential use combination immune checkpoint inhibitors which may have a more potent anti-tumor effect.

### 1.2. Secondary Objectives

The secondary objectives of the trial include:

- Assess response rates to neoadjuvant atezolizumab
  - Objective response rate following completion of neoadjuvant therapy based on RECIST 1.1 criteria
  - Pathological response rate (major and complete pathological response) in final surgical resection specimen
- Assess change in surgical plan, as measured by intensity of surgery performed, cost of care, surgical margins, or vital structures preserved, following neoadjuvant treatment
- Assess safety and tolerability of neoadjuvant atezolizumab

### 1.3. Exploratory Objectives

The exploratory objectives of this study are:

- Perform correlative studies to assess pre-treatment biological markers, including PD-L1 expression, that are associated with response to atezolizumab
- Evaluate tumors prior to and during treatment to identify neoantigen profile changes and T-cell receptor repertoire changes
- Evaluate changes in cell-free DNA, cytokine profiles associated with immune system activation, and lymphocyte subpopulations before and during treatment
- Analysis of genes or gene signatures associated with tumor immunobiology

## 2. BACKGROUND

### 2.1 Study Disease

Cutaneous squamous cell carcinoma (cSCC) is the second most common skin cancer in the US, with over 700,000 cases diagnosed annually, and the incidence is likely to continue to rise. While most cases are successfully treated with ablation or minor surgical resection, approximately 2-4% of patients can present with large recurrences, deeply invasive local disease, extensive perineural invasion, or regional metastases. In these cases of advanced disease, wide surgical resection, lymph node dissection, and reconstructive surgery are often necessary, and usually followed with adjuvant radiation therapy. Despite this aggressive treatment approach, multiple studies of advanced cSCC in the U.S. have shown recurrence rates that range from 28-42%, and OS rates that range from 22-54%. Accurate estimates of the mortality burden are elusive since cSCC is not captured by national cancer registries, however estimates vary from 2,000 to 15,000 annual deaths in the U.S. (Karla, Ansouri, ASCO)

In addition, since 80% to 90% of these lesions occur in the head and neck, even smaller lesions can leave patients with significant disfigurement and a decreased quality of life. Cosmetically sensitive regions such as the nose, eyelids, and ear are very challenging to reconstruct when >50% of the structure is removed. Functionally sensitive regions such as the orbital region or lower lip can be significantly distorted causing drooling, impaired vision, or corneal exposure. In rare cases, the cancer may require removal of the orbital contents leaving a patient with monocular vision. Multiple studies have shown the significant distress, anxiety, and psychological impact of such outcomes. (Moolenburgh, Radiotis)

This study will consider patients who have clinically advanced disease with increased risk of recurrence, and patients with disease for which surgery would result in significant disfigurement or functional impairment (see Inclusion Criteria).

### **Inhibition Of Pd-1/Pd-L1 Pathway In Cutaneous Squamous Cell Carcinoma**

Cutaneous squamous cell carcinoma most often arises in areas of high sun exposure. cSCC has among the highest tumor mutational burden (45.2 mutations/Mb) due to cumulative ultraviolet light-induced mutations. (Walter) This high mutational burden is believed to lead to increased immunogenicity due to the very high expression of neoantigens. (Martincorena) This makes cSCC, similar to other cutaneous malignancies such as malignant melanoma and Merkel cell carcinoma, a particularly attractive target for immunotherapeutic approaches.

Studies have shown the impact of targeting the PD-1/PD-L1 pathway in cSCC, and found favorable results compared to the relatively low response rates of cytotoxic chemotherapy (cisplatin) and anti-EGFR antibodies, with ORR < 30%. The most significant study was for cemiplimab, which received FDA approval for the treatment of locally advanced or metastatic cSCC in patients who were not eligible for curative surgery or radiation. In this study, cemiplimab, an IgG4 anti-PD-1 monoclonal antibody, was found to have an ORR of 46.7%, with duration of response exceeding 6 months in 61% of patients. (Migden)

Other PD-1/PD-L1 checkpoint inhibitors have shown promising activity in cSCC in small cases series, leading to additional larger trials in the locally advanced and recurrent/metastatic populations. Nivolumab (NCT04204837), pembrolizumab (NCT03284424, NCT02883556), and avelumab in combination with cetuximab (NCT03944941) are three such inhibitors with further studies underway. Additional studies of cemiplimab (NCT03969004) and pembrolizumab (NCT03833167) are being performed in the adjuvant setting following surgery and radiation therapy for advanced lesions

## **2.2 Study Agent/Device/Procedure**

### **Background on Atezolizumab**

Atezolizumab is a humanized immunoglobulin (Ig) G1 monoclonal antibody that targets PD-L1 and inhibits the interaction between PD-L1 and its receptors, PD-1 and B7-1 (also known as CD80), both of which function as inhibitory receptors expressed on T cells. Therapeutic blockade of PD-L1 binding by atezolizumab has been shown to enhance the magnitude and quality of tumor-specific T-cell responses, resulting in improved anti tumor activity (Fehrenbacher et al. 2016; Rosenberg et al. 2016). Atezolizumab has minimal binding to Fc receptors, thus eliminating detectable Fc-effector function and associated antibody-mediated clearance of activated effector T cells.

Atezolizumab shows anti-tumor activity in both nonclinical models and cancer patients and is being investigated as a potential therapy in a wide variety of malignancies. Atezolizumab is being studied as a single agent in the advanced and adjuvant settings, as well as in combination with chemotherapy, targeted therapy, and cancer immunotherapy.

Atezolizumab is approved for the treatment of non-small cell lung cancer, small-cell lung cancer and Alveolar Soft Part Sarcoma (ASPS). The PD-L1 inhibitors including atezolizumab have been evaluated in head and neck squamous cell carcinoma and shown to have benefit in early stage trials ([name], Segal). Its safety, tolerability, efficacy, and immunogenicity in adults with advanced solid tumors was evaluated in a phase I/II global, multicenter, open-label, first-in-human dose-escalation and expansion study. In two different trials, atezolizumab in combination with NT-I7 (rhIL-7-hyFc) (NCT03901573) and in combination with cobimetinib (NCT03108131) is currently being investigated for advanced refractory tumors including cSCC.

Details concerning atezolizumab's clinical development can be found in the investigator brochure.

### **For clinicaltrials.gov compliance**

This study will NOT require an Investigational New Drug application (IND). It is considered IND exempt.

## **2.3 Rationale**

Encouraging clinical data emerging in the field of tumor immunotherapy have demonstrated that therapies focused on enhancing T-cell responses against cancer can

result in a significant survival benefit in patients with advanced malignancies (Hodi et al. 2010; Kantoff et al. 2010; Chen et al. 2012).

There are several benefits of a neoadjuvant approach to cSCC. Given the critical location of these lesions and the impact on patients from disfigurement and functional impairment, minimizing tissue resection while not compromising outcomes is an important goal of treatment. Reduction in surgical margins in responders may significantly impact a patient's quality of life and patient reported outcomes.

While the most aggressive cSCCs have been treated with adjuvant chemotherapy, use of immune checkpoint inhibitors may have a distinct advantage for being used in the neoadjuvant setting. Inhibition in the presence of a large tumor mass may theoretically be a more ideal time to prime the system and potentially induce a stronger and broader tumor-specific T-cell response. (O'Donnell) Given the significant recurrence rates and mortality associated with advanced cSCC, future studies could assess if this immune response can increase DFS and may ideally select which patients benefit from further treatment in the adjuvant setting. Neoadjuvant window of opportunity trials also provide a unique opportunity to study biological correlates and markers of response in surgically curable disease.

The experience with neoadjuvant treatment is growing. A study of neoadjuvant nivolumab in untreated, surgically resectable early stage non-small cell lung cancer enrolled 22 patients, of which 20 patients were able to complete the 2 cycles of therapy. (NCT02259621) Among these patients, 45% had a major pathological response, and none of the patients had any treatment-related delays in surgery. 20 of 21 patients were able to undergo complete surgical resection. (Forde)

A pilot study in cSCC was presented at the 44th European Society of Medical Oncology in 2019 using 2 doses of neoadjuvant cemiplimab for patients with Stage 3 and 4 cSCC of the head and neck. (NCT03565783) In this study of 20 patients, the treatment was well tolerated with no grade 3 or 4 AEs. 55% of patients achieved a pathological complete response and 15% of patients achieve a major pathological response (<10% viable tumor). All patients were able to proceed with anticipated curative surgical resection. (Gross)

In addition to this trial, other studies have shown a neoadjuvant approach is feasible with cutaneous malignancies and can result in decreased surgical defects. Blank et. al. examined neoadjuvant versus adjuvant ipilimumab plus nivolumab in macroscopic stage III melanoma and found that all of the patients in the neoadjuvant treatment arm were able to undergo the anticipated surgery. Of the 9 patients evaluable in the neoadjuvant arm, 78% achieved a significant pathological response and majority had a decrease in lesion size. In a trial of vismodegib used in a neoadjuvant fashion prior to treatment of high-risk basal cell carcinoma, surgical defect size was reduced by 27% in patients who were able to complete 3 months of treatment with all patients able to complete surgical resection. (Ally)

The risks of this trial, similar to other neoadjuvant trials, include the possibility of disease progression resulting in either a more extensive resection than initially anticipated or loss of opportunity for curative surgery. Encouraging data from a preliminary study (NCT03565783, Gross) showed that the risk of this is likely low and worth the potential opportunity to reduce lesion size. This risk will be minimized by careful monitoring of visible lesions following each cycle, and also includes an additional imaging study after the second dose of atezolizumab to check for radiographic evidence of disease progression.

The toxicity profile for atezolizumab is expected to be similar to its use for other indications. Atezolizumab has been generally well tolerated. Adverse events with potentially immune-related causes consistent with an immunotherapeutic agent, including rash, influenza-like illness endocrinopathies, hepatitis or transaminitis, pneumonitis, colitis, and myasthenia gravis, have been observed (see Atezolizumab Investigator's Brochure for detailed safety results). To date, these events have been manageable with treatment or interruption of atezolizumab treatment.

This trial will enroll patients with advanced cutaneous squamous cell carcinoma. Given the significant rates of recurrence and mortality, in addition to the disfigurement and functional impairment resulting from aggressive treatment, this population is considered appropriate for trials of novel therapeutic candidates. This feasibility study will be the first step towards designing a larger trial that examines surgical margin reduction, disease recurrence rates, and optimal adjuvant therapy strategies. If feasible, this study may also test the feasibility of this strategy for use of different combination regimens in the future.

## 2.4 Study Design

An overview of the study is provided in the study flowchart (Section 9). Briefly, upon eligibility confirmation and study enrollment, subjects will undergo initial tumor biopsy and receive neoadjuvant atezolizumab (1200 mg). Atezolizumab will be administered by intravenous (IV) infusion at a fixed dose of 1200 mg on Day 1 (+/- 3 days) of each 21-day cycle for a total of 3 doses prior to surgery, unless there is clinical or radiographic evidence of disease progression. If clinically feasible, an additional biopsy will be performed after the first dose for biological correlative studies. Patients will be seen prior to each cycle to assess response. A formal assessment including imaging of the head and neck will be performed after 2 cycles of treatment. After the third dose, standard of care surgical resection will be performed. AEs will be assessed up to 30 days after surgical resection. Following surgery, adjuvant therapy will be administered per the standard of care, which includes radiation therapy for AJCC Stage 3 and 4 disease.

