#### **7.3.1 Adverse Event Reporting Period**

The study period during which all AEs and SAEs must be reported begins after informed consent is obtained and initiation of study treatment and ends 30 days following the last administration of study treatment or study discontinuation/termination, whichever is earlier. After this period, investigators should only report SAEs that are attributed to prior study treatment.

All adverse events (AEs), regardless of seriousness or relationship to study drug, are to be collected only on designated study dates from signing of informed consent through 30 days after administration of study drug, and recorded in the study-specific worksheets, with the following exceptions:

- AEs that are solely laboratory values; are not related to the study drug; AND are clinically non-significant may not be collected.
- Non serious AEs that are not related to the study drug; are not clinically significant; AND are expected in the post-surgery clinical setting may not be collected.
- SAEs that occur from signing of informed consent to prior to administration of study agent may not be collected unless assessed as possibly, probably or definitely-related to a study procedure.

All patients enrolled in this study receive surgical intervention in the course of their standard of care. As a consequence of this surgery, patients may experience certain

expected and normal adverse events. The following post-operative adverse events will be captured only in the patient's Electronic Health Record (EHR) source documentation and not in the adverse event log. If the adverse event exceeds the grading listed below or occurs outside the post-operative time window, the adverse event will be recorded in the Adverse Event Logs.

- Surgical wound site and associated, expected secondary signs and symptoms, including:
  - CTCAE v5.0 Grade 1 pain associated with surgical wound, including headaches – mild pain, little to no limit on adult daily life.
  - CTCAE v5.0 Grade 1 weight loss, anemia, and electrolyte abnormalities.

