- s Patients will undergo clinical tumor assessments at baseline and once per cycle. All measurable and evaluable lesions should be re-assessed at each subsequent tumor evaluation. **RECIST measurements are only required at baseline, after cycle 2, and ORR can be assessed after cycle 2/surgery.**
- t Medication (e.g., prescription drugs, over-the-counter drugs, vaccines, herbal or homeopathic remedies, nutritional supplements) used by a patient in addition to protocol-mandated treatment from 7 days prior to initiation of study treatment until the treatment discontinuation visit.
- u After informed consent has been obtained but prior to initiation of study treatment, only serious adverse events caused by a protocol-mandated intervention should be reported. After initiation of study treatment, all adverse events will be reported until 30 days after the last dose of study treatment or until initiation of new systemic anti-cancer therapy, whichever occurs first, and serious adverse events and adverse events of special interest will continue to be reported until 90 days after the last dose of study treatment or until initiation of new systemic anti-cancer therapy, whichever occurs first. After this period, all deaths, regardless of cause, should be reported. In addition, Genentech, Inc. should be notified if the investigator becomes aware of any serious adverse event that is believed to be related to prior exposure to study treatment (see Section 5.6). The investigator should follow each adverse event until the event has resolved to baseline grade or better, the event is assessed as stable by the investigator, the patient is lost to follow-up, or the patient withdraws consent. Every effort should be made to follow all serious adverse events considered to be related to study treatment or trial-related procedures until a final outcome can be reported.

	Screening a	Treatment Cycles (21-day cycles)					Surgery	Follow-Up (or Treatment Discontinuation b )
		Cycle 1		Cycle 2		Cycle 3		
	Within 28 days prior to start of treatment	Day 1 ( $\pm$ 3 days)	Day 14 ( $\pm$ 7 days)	Day 21 ( $\pm$ 3 days)	Day 38 ( $\pm$ 4 days)	Day 42 ( $\pm$ 3 days)	2-4 weeks after Cycle 3	10 days $\pm$ 5 days after surgery (or < 30 days after last treatment)

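### After day 30 from the last dose, Section 7.3.1 and calendar footnote u give conflicting rules for SAEs and deaths; the Section 2.4 overview also ends all-AE assessment on a different date

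*Combined protocol and SAP*

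**What the plan says.** Four parts of the current protocol set the end of safety follow-up.

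- **Section 2.4 (overview).** "After the third dose, standard of care surgical resection will be performed", and then "AEs will be assessed up to 30 days after surgical resection".
- **Section 7.3.1 (reporting period).** The period for all AEs and SAEs "ends 30 days following the last administration of study treatment or study discontinuation/termination, whichever is earlier". From then on: "After this period, investigators should only report SAEs that are attributed to prior study treatment". The same section says that AEs "are to be collected only on designated study dates from signing of informed consent through 30 days after administration of study drug". It keeps certain Grade 1 post-operative events out of the AE log unless the event exceeds that grade or "occurs outside the post-operative time window". The length of that window is not given.
- **Section 7.5.2.2 (deaths).** Deaths of any attribution are reportable if they fall within the 7.3.1 period.
- **Section 9, footnote u.** After treatment starts, "all adverse events will be reported until 30 days after the last dose of study treatment or until initiation of new systemic anti-cancer therapy", whichever comes first. Then "serious adverse events and adverse events of special interest will continue to be reported until 90 days after the last dose of study treatment", again unless new systemic anti-cancer therapy starts sooner. After that, deaths of any cause are to be reported, and SAEs believed related to treatment are to be notified.

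The calendar puts surgery two to four weeks after Cycle 3 and schedules one post-operative AE assessment, 10 ± 5 days after surgery. Safety and tolerability is a secondary objective (Section 1.2).

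**The concern.** Sections 7.3.1 and 7.5.2.2 and footnote u are all operative text. Section 7.3.1 says that only attributed SAEs are to be reported after day 30, so it sets a limit, not a minimum that footnote u extends. The documents contain no clause saying which text prevails. Two staff members could handle the same patient differently and each be following the protocol.

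What is at stake is the completeness of the post-operative safety record. Section 10.1 says that the postponement of surgery must be shown not to harm the chance of curative treatment, and makes a possible further cohort depend on that. Serious operative events bear on that question even when they are judged unrelated to atezolizumab, and those are the events on which the texts disagree.

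**Working it through.** The plan gives no figure to reproduce here. The check sets the rules side by side and then does date arithmetic.

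**Rules by event class** (days counted from the last dose)

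| Event class | Section 2.4 | 7.3.1 and 7.5.2.2 | Footnote u |
|---|---|---|---|
| All AEs | 30 days after resection | day 30 | day 30 |
| Unattributed SAEs | not separated from AEs | day 30 | day 90 |
| Attributed SAEs | not separated from AEs | no time limit | no time limit |
| AESIs | not separated from AEs | day 30, then only if an attributed SAE | day 90 |
| Unattributed deaths | not separated from AEs | day 30 | no time limit |
| Early stop | none stated | study discontinuation or termination | new systemic anti-cancer therapy (does not stop reporting of deaths or related SAEs) |

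The operative texts agree on all AEs and on attributed SAEs. They disagree on unattributed SAEs for days 31 to 90 (90 − 30 = 60 days), on unattributed deaths from day 31 onward, and on the early stop. The early-stop difference can arise in practice, because the prohibited-therapy text in Section 4.7.2 permits adjuvant systemic therapy after resection.

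**Dates for all AEs**

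Inputs: dose 3 is day 0 (calendar Day 42). Surgery is on day s = 14 to 28. This assumes that the calendar's two to four weeks run from the third dose, as Section 2.4 suggests.

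- Cut-off in 7.3.1 and footnote u: day 30 (calendar Day 42 + 30 = 72).
- End of the Section 2.4 period: s + 30 = day 44 to 58 (calendar Day 86 to 100).
- Difference: (s + 30) − 30 = s = 14 to 28 days.
- Post-operative days inside the cut-off: 30 − s = 16 down to 2. As shares of 30: 16/30 = 53% and 2/30 = 7%.
- Post-operative AE visit, nominal: s + 10 = day 24 to 38. It falls after day 30 when s is 21 or more.
- Stretch of the Section 2.4 period with no scheduled AE date after that visit: 30 − 15 = 15 to 30 − 5 = 25 days.

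**Example.** Surgery is on day 21. A complication starts on day 35 (post-operative day 14), is fatal on day 41 (post-operative day 20), and is judged unrelated to atezolizumab. No new systemic therapy has started.

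- Section 2.4: inside, since its period ends on day 21 + 30 = 51.
- Footnote u: inside, since 35 and 41 are both below 90.
- Section 7.3.1: outside, since onset is after day 30 and the event is not attributed.
- Section 7.5.2.2: outside, since the death is after day 30.

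**The case against.** Much can be said for the plan.

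- **Section 2.4 is a brief overview that points to Section 9.** The two operative passages agree on the all-AE limit. This stands: the all-AE discrepancy is one overview sentence against two consistent rules, and it is the lesser part of the point.
- **Open events are not lost.** Footnote u follows each AE until it resolves, stabilises, or the patient is lost or withdraws. This stands, and it is why the example needs onset after day 30.
- **AESIs have their own rule.** Section 7.2.3 requires AESIs to be reported whether or not they are serious, and sets no time limit. A reader might infer from 7.3.1 that AESIs are lost for 60 days; 7.2.3 largely removes that inference.
- **Some post-operative AEs are left out on purpose.** Section 7.3.1 exempts certain expected, unrelated, non-serious events and sends listed Grade 1 events to the health record only. Not every non-serious post-operative AE after day 30 is therefore an unintended loss.
- **Other text covers part of the gap.** Section 7.2 includes all deaths in the safety assessments without naming a period, and Section 11.2 has the investigator monitor AEs continuously. These help, but neither overrides the express limit in 7.3.1.
- **Drug-related safety is protected.** Attributed SAEs stay reportable without a time limit under 7.3.1, 7.5.2.7 and footnote u, and Section 12.6 sets out no safety analysis that would change. This stands, and it limits the consequence.

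A reader might also count surgery from the end of the 21-day third cycle. Surgery would then fall on days 35 to 49, which is 5 to 19 days after all-AE collection has closed. The documents do not support that as the natural reading: Section 2.4 places surgery after the third dose, and 7.3.1 has rules for logging post-operative AEs that would then have little purpose. The calendar heading is still loose enough to need confirming.

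**Conclusion.** The contradiction is real, and it lies mainly between operative sections. After day 30 from the last dose, 7.3.1 and 7.5.2.2 exclude new-onset unattributed SAEs and deaths that footnote u requires: for 60 days in the case of SAEs, and without limit in the case of deaths. The early-stop clauses also differ. The Section 2.4 discrepancy on all AEs is secondary. It amounts to 14 to 28 days per operated patient if surgery is counted from dose 3. On 8 of the 15 permitted surgery days (21 to 28), the only post-operative AE visit nominally falls after the cut-off. That is a count of dates, not a probability.

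No event rate can be derived from the documents. With 20 evaluable patients, one inconsistently captured event moves a reported rate by 1/20 = 5 percentage points.

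A reader might infer that the feasibility result or the enrolment hold is compromised. The documents do not support that. The primary outcome is fixed at the time of surgery, and sample size and power do not depend on these windows. The hold in Section 7.2 concerns events attributed to checkpoint inhibitor treatment and draws on all patient safety data. The point should be corrected, but the main conclusion of the trial does not turn on it.

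**What to change.** 1. **SAEs, AESIs and deaths.** Amend 7.3.1 and 7.5.2.2 to match footnote u: all SAEs and AESIs to 90 days after the last dose whatever the attribution, deaths of any cause as in footnote u, and attributed SAEs without a time limit.
2. **Early stop.** State one rule in both 7.3.1 and footnote u, replacing the discontinuation/termination clause in 7.3.1. Say that it does not end reporting of attributed SAEs or deaths.
3. **All AEs.** Choose one end date and use it in 2.4, 7.3.1 and footnote u. The preferred choice is 30 days after resection, or 30 days after the last dose if there is no surgery. With it, either lift the restriction to designated study dates for post-operative events or add a telephone check on post-operative day 30. The alternative is to cut the Section 2.4 sentence to match the other two and let the 10 ± 5 day visit count even when it falls after day 30. Items 1 and 2 are needed with either choice.
4. **Definitions.** Give the post-operative window of 7.3.1 in days, and have the sponsor confirm whether the calendar's surgery interval runs from the third dose.

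The cost is wording in 2.4, 7.3.1, 7.5.2.2 and footnote u, plus clarification of one calendar heading. The longer all-AE period adds 14 to 28 days of collection per operated patient (surgery counted from dose 3). If the telephone check is chosen, it means about 20 calls. No patient and no clinical procedure is added.
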